Gene expression profiles	RNA sequencing or other transcriptional profiling methods, including, but not limited to TCR or BCR repertoire analysis
Nasal antibody response	IgG and/or IgA ELISA in nasal secretions
Hemagglutination inhibition	HAI assays

BCR = B cell receptor; bnAbs = broadly neutralizing antibodies; ELISA = enzyme-linked immunosorbent assay; Fc = fragment crystallizable; HA = hemagglutinin; HAI = hemagglutination inhibition; Ig = immunoglobulin; RNA = ribonucleic acid; TCR = T cell receptor.

ILI Procedures

For the duration of the influenza season, participants will be followed-up to identify potential cases of influenza virus infection. During the influenza season, participants should record any signs and symptoms of ILI (such as cough, sore throat, headache, nasal congestion, feeling feverish, body aches and pains, fatigue, or neck pain), including measurement of body temperature, on a daily basis until symptoms have resolved using a specific Flu-iiQ™ questionnaire and an ILI form.

If ILI symptoms develop during the influenza season, the following should take place:

- Participants should contact the site as soon as possible to notify the site of ILI.
- Participants should record signs and symptoms of the ILI daily using the Flu-iiQ™ questionnaire from onset of symptoms until the day of symptom resolution, and record body temperature daily using an ILI form provided by the sponsor until the day of symptom resolution.
- Participants should take a nasal sample at home on the day of symptom onset or the day thereafter (ILI Days 1-2). The sample should be stored refrigerated and brought to the site by the participant within 4 days (preferably) after collection.
- Participants should go to their study site, ideally between 2 and 4 days after symptom onset (ILI Days 3-5), where
 - the completed Flu-iiQ™ questionnaire and ILI form will be collected and reviewed by site staff;
 - the participant nasal self-swab sample (taken on ILI Days 1-2) will be collected;
 - an additional nasal swab will be taken by a qualified member of the site staff;
 - the presence of influenza virus infection will be assessed by qualified site staff by RT-PCR diagnostics and/or rapid-PCR detection (eg, by Cepheid GeneXpert®) on the nasal swab samples mentioned above;
 - a blood sample for seroconfirmation of influenza virus infection will be taken by a qualified member of the site staff;
 - and vital signs, including body temperature, blood pressure, heart rate, respiratory rate and oxygen saturation, will be measured by a qualified member of the site staff. A clinical assessment, including a targeted physical examination, will be completed by qualified site staff, preferably by a physician, physician assistant, nurse practitioner, or equivalent.

- At ILI Day 29 (± 7 days), participants will be asked to return to the site where
 - the completed Flu-iiQ™ questionnaire and ILI form will be collected and reviewed by site staff;
 - a blood sample for seroconfirmation of influenza virus infection will be taken by a qualified member of the site staff;
 - and vital signs, including body temperature, blood pressure, heart rate, respiratory rate and oxygen saturation will be measured by a qualified member of the site staff. A clinical assessment (including a targeted physical examination) will be performed by qualified site staff, preferably by a physician, physician assistant, nurse practitioner, or equivalent.
- For all medically attended ILIs, including those resulting in hospitalization, additional information on any other diagnostics (eg, chest x-rays, spirometry, pulmonary function tests) or interventions during the clinical course of ILI will be collected.

During the influenza season, participants will be contacted by telephone or other means of communication approximately every 14 ± 3 days (unless a planned visit has occurred or will occur within 14 days). These calls will remind participants to complete the Flu-iiQ™ questionnaire and ILI form in the event of any symptoms of ILI, and to contact the site and to take a nasal sample at the time of symptom onset. These calls will also check for any SAEs, and associated concomitant medications since the previous visit or telephone contact.

The presence of influenza virus will be assessed by site by RT-PCR diagnostics on the nasal swab samples, which may include viral load and influenza subtyping. In addition, blood samples from participants with a suspected ILI will also be assayed by serology by the sponsor (including but not limited to HAI assay as available and applicable) for influenza virus exposure confirmation. The blood samples may additionally be used to evaluate immune responses during the ILI.

Every effort should be made to collect data on the clinical course of ILIs including information on hospitalization, oxygenation status, supplemental oxygen requirements and specific drug treatments, as well as other concurrent respiratory illness present at the time of the diagnosis of the event and up to symptom resolution.

For participants who experience symptoms suggesting ILI, RT-PCR assay of the nasal swabs taken after symptom onset will be used to determine whether the infection was caused by influenza virus. For participants hospitalized with symptoms of ILI, confirmation of influenza virus infection using RT-PCR may be performed at the local (hospital) laboratory.

Any ILI and complications related to ILIs will be reported as an AE if it occurs between the time of any vaccination through the following 28 days. An ILI and complications related to ILIs that occur outside of this period does not require AE reporting unless ongoing at the time of subsequent vaccination. Any ILI and complications related to ILIs fulfilling the criteria of an SAE will be reported as such during the entire study period from the first vaccination.

SAFETY EVALUATIONS

On a daily basis, for 7 days after each vaccination, participants will be asked to record symptoms of the following AEs via the participant diary:

- Solicited injection site AEs: erythema (measured using the ruler supplied), swelling (measured using the ruler supplied), and pain/tenderness.

- Solicited systemic AEs: fatigue, headache, myalgia, nausea and fever (ie, body temperature ≥ 38 °C [100.4°F]).

Oral temperature should be measured at approximately the same time each day, preferably in the evening, using the thermometer supplied. Temperature 7 days after each vaccination may be collected earlier on the Day 8 or Day 64 to coincide with the clinic visit.

Adverse events and special reporting situations, whether serious or non-serious, that are related to study procedures or that are related to non-investigational sponsor products will be reported from the time a signed and dated ICF is obtained until the end of the study/early withdrawal.

Solicited AEs, collected through a diary, will be recorded for each vaccination from the moment of vaccination until 7 days post-vaccination.

All other unsolicited AEs and special reporting situations, whether serious or non-serious, will be collected for each vaccination from the moment of vaccination until 28 days post-vaccination. Unsolicited AEs with the onset date outside the timeframe defined above (>28 days after previous study vaccination), which are ongoing on the day of the subsequent vaccination, should be recorded on the electronic case report form (eCRF) AE page.

All SAEs and AEs leading to discontinuation from further study vaccination (regardless of the causal relationship) are to be reported from the moment of first vaccination until completion of the participant's last study-related procedure, which may include contact for safety follow-up. The sponsor will evaluate any safety information that is spontaneously reported by an investigator beyond the time frame specified in the protocol.

STATISTICAL METHODS

Sample Size Determination

With 25 participants per active regimen arm, the observation of no vaccine reactions after the first vaccination would be associated with a 95% confidence that the true rate is less than 11.3%. Across active regimens (N=150), the observation of 0 vaccine reactions after the first vaccination would be associated with a 95% confidence that the true rate is less than 2.0%.

Populations for Analyses

For purposes of analysis, the following populations are defined:

- Full Analysis Set (FAS): The FAS will include all participants with at least one vaccination documented.
- Per-protocol Immunogenicity (PPI): The PPI Set will include all randomized and vaccinated participants for whom immunogenicity data are available excluding samples taken on or after the date when a participant experiences a major protocol deviation expected to impact the immunogenicity outcomes.

Primary Endpoints

No formal statistical testing of safety data is planned. Safety data will be analyzed descriptively per study group, with special attention for SAEs, Grade 3/4 AEs, and AEs leading to discontinuation of study vaccine. All safety analyses will be made on the FAS.

Secondary Endpoints

No formal hypothesis on immunogenicity will be tested. Descriptive statistics (geometric mean and 95% confidence interval, or median and quartile range [Q1-Q3], as appropriate) will be calculated for continuous immunological parameters at all time points and for changes from baseline. Graphical representations of immunological parameters will be made as applicable. Frequency tabulations will be calculated for discrete (qualitative) immunological parameters as applicable. The immunogenicity analyses will be performed on the PPI set. An additional analysis might be done for the FAS.

Planned Analyses

The primary analysis will occur when all participants have completed the 28 days post-Dose 2 visit or have discontinued earlier. These analyses will include immunogenicity data on quantification of antibody binding to full-length HA and HA stem protein and safety data up to the 28 days post-Dose 2 visit. At the time of the primary analysis, the study will be unblinded for sponsor and external partnerships personnel who are involved in the data analysis and decision making. Participants and study-site personnel will remain blinded to the study vaccine allocation until the end of the study.

[figure not shown]
An additional analysis will occur when all participants have completed the 6-month post-Dose 2 visit or discontinued earlier. These analyses will include additional safety data up to the 6 months post-Dose 2 visit and immunogenicity data required per the sponsor's assessment. This analysis may allow to evaluate persistence of immune responses.

No study modifications are planned as a result of primary or additional analyses. The exact scope of each analysis will be defined based on the availability of immunogenicity data and findings from previous analyses. Additional interim analyses may be performed during the study for the purpose of informing future vaccine development-related decisions in a timely manner, or upon health authority request. If required, these unplanned interim analyses may replace or be combined with planned analyses, depending on the timing.

The final analysis will occur when the last participant has completed the final visit of the schedule of assessment (Day 365±30 days) or discontinued earlier. Final analyses will allow for determination of the durability of the immune response and analyze any additional safety and immunological data collected after the additional analysis.

1.2. Schema

Figure 1: Schematic Overview of the Study for all Cohorts

* Participants will be enrolled in a staggered approach with safety evaluations (Day 8) in place before extending enrollment in each cohort and progressing from one cohort to the next.

Further information on the overall design of the study can be found in Section 4.1, Overall Design.

1.3. Schedule of Activities (SoA)

1.3.1. Schedule of Activities – Assessments for all Participants

Clinic Visit #	1	2	3	4	5	6	7	8	9	Early Exit ^a
Visit Timing		Vac 1	Vac 1 + 7 d	Vac 1 + 28 d	Vac 2	Vac 2 + 7 d	Vac 2 + 28 d	Vac 2 + 6 mo	Vac 1 + 12 mo	
Visit Day and Window	-42 to 1 ^b p	1 ^{b,p}	8 ^c +2 d	29 ^c ±3 d	57 ^b ±3 d	64 ^c +2 d	85 ^c ±3 d	238 ^c ±14 d	365±30 d	
Visit Type	Screening	VAC 1	Safety and immuno.	Safety and Immuno.	VAC 2	Safety and immuno.	Safety and Immuno.	Safety and Immuno.	Safety and Immuno.	Early exit
Written informed consent form (ICF) ^d	●									
Inclusion/exclusion criteria	●									
Demographics	●									
Medical history/prestudy meds	●									
Physical examination ^e	●	①			①					
Vital signs ^f incl. body temperature	●	②	●	●	②	●	●		●	●
Serum pregnancy test (female participants of childbearing potential) ^g	● 2.5									
Urine pregnancy test (female participants of childbearing potential)		①			①					
Randomization		①								
Verification of selected eligibility criteria ^g		①			①					
Pre-vaccination symptoms ^h		①			①					
Serology blood sample (HAI), mL ⁱ		① 4								
Hematology ⁱ	● 2	① 2	● 2		① 2	● 2				
Clinical Chemistry ⁱ	● 3	① 3	● 3		① 3	● 3				
Humoral immunogenicity sample (serum), mL ⁱ		① 30	● 10	● 30	① 10	● 10	● 30	● 30	● 30	③ 30
Transcriptome (PAXgene [®]) sample, mL		① 2.5	● 2.5			● 2.5				④ 2.5
Nasosorption sample (SAM)		①		●			●	●		●
Vaccination		●			●					
30-minute post-vaccination observation ^j		●			●					
Solicited AE recording			Continuous		Continuous					④
Unsolicited AE recording ^k			Continuous		Continuous					⑤
SAE recording ^k					Continuous					●
Concomitant medications ^l					Continuous					●
Influenza infection ^m					Continuous					
Participant Wallet Card distribution	●									
Participant diary distribution and training		●			●					
Distribution and training of rulers and thermometers ⁿ		●			●					

Clinic Visit #	1	2	3	4	5	6	7	8	9	
Visit Timing		Vac 1	Vac 1 + 7 d	Vac 1 + 28 d	Vac 2	Vac 2 + 7 d	Vac 2 + 28 d	Vac 2 + 6 mo	Vac 1 + 12 mo	Early Exit ^a
Visit Day and Window	-42 to 1 ^b	1 ^{b,p}	8 ^{c+2} d	29 ^{c±3} d	57 ^{b±3} d	64 ^{c+2} d	85 ^{c±3} d	238 ^{c±14} d	365±30 d	
Visit Type	Screening	VAC 1	Safety and immuno.	Safety and Immuno.	VAC 2	Safety and immuno.	Safety and Immuno.	Safety and Immuno.	Safety and Immuno.	Early exit
Flu-iiQ™ questionnaire and ILI form distribution ^m						To be distributed before the start of the influenza season				
Nasal swab kit and insulated cooler bag training and distribution						To be distributed before the start of the influenza season				
Participant diary review by qualified site staff ^{c,o}			●			●				
Blood Draw Volumesⁱ:										
Participants in the main study										
Approximate daily blood draw, mL	7.5	41.5	17.5	30	15	17.5	30	30	30	32.5
Approximate cumulative study blood draw, mL	7.5	49	66.5	96.5	111.5	129	159	189	219	–

^a 1 pre-dose; ^b pre- and post-dose; ^c blood samples for immunogenicity will only be taken if the early exit is at least 14 days after the previous immunogenicity blood draw; ^d if within 7 days of the last vaccination; ^e if within 28 days of the last vaccination

- For those participants who are unable to continue participation in the study up to Day 365±30 days, but for whom consent is not withdrawn, an exit visit will be conducted as soon as possible.
- An additional telephone call will be made to sentinel participants 48 hours post-vaccination to collect safety information. A phone call or other means of communication should be made to all participants 3 to 5 days after Day 1 and Day 57 visits to ensure that participants are completing the diary without issues.
- It is important to calculate visit window for Day 8, Day 29, Day 64, Day 85 and Day 238 visits with respect to the last vaccination visit. For example, Day 64 should be calculated with respect to vaccination 2 = VAC 2 + 7 days (+ 2 days window), and not as 64 days (+ 2 days window) after vaccination 1. If any of the participants for the 7-day post-dose safety review come in earlier than Day 8 for Visit 3 or Day 64 for Visit 6 (which will be a protocol deviation), a subsequent phone call will be made at the end of the diary period to collect diary card information recorded between the actual visit and the end of the 7-day post-dose diary period on Day 8 and Day 64, respectively.
- Signing of the ICF should be done before any study-related activity.
- A full physical examination, including height and body weight, will be carried out at screening. At other visits, an abbreviated, symptom-directed examination will be performed if determined necessary by the investigator. A symptom-directed physical examination may be repeated if deemed necessary by the investigator.
- Supine systolic and diastolic blood pressure, heart rate and respiratory rate after at least 5 minutes rest. It is recommended that vital signs are measured before blood draws.
- To include inclusion criteria [4](#), [6](#) and [8](#), and exclusion criteria [2](#), [8](#), [9](#), [10](#), [13](#), [14](#), and [21](#).
- Investigator must check for acute illness or body temperature $\geq 38.0^{\circ}\text{C}$ (100.4°F) at the time of vaccination. In such cases, the participant may be vaccinated up to, and no later than 10 days after the scheduled vaccination, or be withdrawn at the discretion of the investigator.
- Blood sample volumes are approximate. Refer to the central laboratory manual or requirements of local laboratories for additional details. Additional blood samples may be collected for safety assessment and participants with influenza-like illness (Section [1.3.2](#), Schedule of Activities – Assessments for Participants With Influenza-like Illness [ILI]).
- Participants will be closely observed for a minimum of 30 minutes post-vaccination. Any unsolicited, solicited injection site and systemic AEs, and vital signs (supine systolic and diastolic blood pressure, heart rate, respiratory rate and body temperature) will be documented by study-site personnel following this observation period.
- All AEs and special reporting situations, whether serious or non-serious, that are related to study procedures or that are related to non-investigational (concomitant) sponsor products will be reported from the time a signed and dated ICF is obtained onwards. All SAEs and AEs leading to discontinuation from further study vaccination, will be reported from the day of first vaccination onwards until the end of the study.

1. Concomitant therapies will be collected from the signing of the ICF until 28 days after the first vaccination and from the second vaccination through the following 28 days, and additionally outside of these periods when associated with an SAE.
- m. Signs and symptoms of influenza infection will be recorded during the influenza season using the Flu-iiQ™ questionnaire and ILI form. Participants will be notified of the influenza season. During the influenza season, they will be contacted by telephone or other means of communication every 14±3 days (unless a prescheduled clinic visit has occurred or will occur within 14 days). Calls will remind participants to complete the Flu-iiQ™ questionnaire and ILI form in the event of any symptoms of ILI, to contact the site and to take a nasal sample at home at the time of symptom onset. Calls will also check for any SAEs and associated concomitant medications since the previous visit or telephone contact. Details of these procedures are described in Section 8.1.1, ILI Procedures.
- n. Ruler and thermometers will be distributed at Day 1 visit, and training will be conducted by the site staff at both Day 1 and Day 57 visits.
- o. Review of diary entries with participants and grading of symptoms must be done by a qualified and delegated site staff member under the oversight of the investigator or a delegated physician. After review of the diary entries with the participant, the investigator or qualified delegate, will complete their own assessment and document in the relevant sections of the eCRF.
- p. In case site staff are able to complete all required screening procedures and determine participant eligibility on the same day (including review of required clinical laboratory results), the screening visit and the Day 1 visit (first vaccination) may occur on the same day (Day 1), and repeat of Day 1 procedures (including physical examination, vital signs, urine pregnancy test, hematology and clinical chemistry) is not required.

AE = adverse event; d = day; Flu-iiQ™ = Influenza Intensity and Impact Questionnaire; HAI = hemagglutination inhibition; ICF = informed consent form; ILI = influenza-like illness; immuno. = immunogenicity; mo = month; SAE = serious adverse event; vac = vaccination; SAM = Synthetic Absorptive Matrix strips.

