For both cohorts, the DRC will review blinded ^b 7-day post-first dose as well as post-second dose safety. Safety data for review will include solicited and unsolicited AEs, SAEs, and available laboratory assessments. If any pre-specified study vaccination pausing rule is met, vaccinations will be paused, and a DRC meeting will be convened. For details on the pausing rules, see [Section 6.8, Study Pausing Rules](#). In addition, the DRC will also evaluate safety data over the course of the study and review any events that meet a specific study vaccine pausing rule or any other safety issue that may arise.

Study Procedures

After each vaccination, participants will remain under observation at the study site for at least 30 minutes for presence of any acute reactions and solicited events. In addition, participants will record solicited signs and symptoms in a diary for 7 days post-vaccination, beginning each study vaccine dosing day. Participants will be given a thermometer, ruler and daily assessment (participant) diary with instructions for the proper recording of events. Oral temperatures should be taken at approximately the same time each day, ^c and additional temperature measurements may be taken if a participant does not feel well. Study-site personnel will collect and review participant diary information and confirm the entries at subsequent site visits.

AEs will be collected as outlined in [Section 8.3.1, Time Period and Frequency for Collecting Adverse Event and Serious Adverse Event Information](#).

^a In case a participant in the sentinel subset or the safety ramp-up subset withdraws from the study prior to receiving Dose 2 or receives Dose 2 outside the prespecified visit window, the post-second dose 48-hour safety review by the PI(s) and SRP, as well as the 7-day safety review by the DRC will be performed as scheduled based on the available data.

^b The DRC will review blinded data first but may review unblinded data if deemed necessary.

^c Temperature 7 days after each vaccination may be collected earlier on the Day 8 or Day 64 to coincide with the clinic visit.

All AEs, including any that are ongoing at 28 days after each dose, will be followed until clinical resolution or stabilization. Concomitant therapies will be collected from the signing of the ICF until 28 days after the first vaccination and from the second vaccination through the following 28 days, and additionally outside of these periods when associated with an SAE.

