6.8. Study Pausing Rules

If a study vaccination is considered to raise significant safety concerns (and a specific set of pausing criteria have been met), further vaccination of participants may be paused after medical review as described below. The concerned data will then be reviewed by the DRC, after which the DRC will recommend whether the pause can be lifted or not, or whether other steps are needed.

1. The occurrence of any of the following events may lead to a pause in further study vaccination. This list is only applicable for concerned AEs that occur up to 4 weeks after each vaccination and for concerned SAEs from the first vaccination throughout the study. Death of a participant, considered related to study vaccine or if the causal relationship to the study vaccine cannot be excluded; OR
Note: All cases of death will be sent for DRC information. Upon their review, DRC may then decide whether a study pause is required.
2. One or more participants experience an SAE, a Grade 4 (solicited or unsolicited) AE, or a persistent (upon repeat testing) Grade 4 laboratory abnormality that is determined to be related to study vaccine; OR
3. One or more participants experience anaphylaxis or generalized urticaria within 24 hours of vaccination, clearly not attributable to other causes than vaccination with study vaccine; OR
4. Three or more participants experience a Grade 3 unsolicited AE of the same type (as per medical judgment of the sponsor), that is determined to be related to study vaccine, that persists for 72 hours or longer; OR one participant from sentinel cohort experiences a Grade 3 unsolicited AE that is determined to be related to study vaccine; OR
5. Three or more participants experience a persistent (upon repeat testing) Grade 3 laboratory abnormality related to the same laboratory parameter and considered related to study vaccine; OR One participant from sentinel cohort experiences a persistent (upon retesting) Grade 3 laboratory abnormality that is determined to be related to study vaccine; OR
6. Three or more participants experience a Grade 3 solicited AE of the same type, determined to be related to study vaccine, and persisting as Grade 3 for longer than 3 consecutive days (ie,

the day of occurrence of the AE is counted as Day 1); OR one participant from sentinel cohort experiences a Grade 3 solicited systemic AE that is determined to be related to study vaccine.

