For number 2 and number 5: to assess abnormal laboratory values, the test must be repeated at least once, within 48 hours of the site becoming aware of the abnormal value.

For number 4, number 5 and number 6: after each DRC review of similar AEs, the Committee will indicate the conditions under which it requires further notification and review of the subsequent similar AEs.

To enable prompt response to a situation that could trigger pausing rules, the investigator should notify the sponsor's medical officer or designee (AND transmit SAE form [if applicable] in a secure manner electronically or by facsimile [fax] to the sponsor), immediately and no later than 24 hours after becoming aware of any related AE of Grade 3 or above AND update the eCRF with relevant information on the same day the AE information is collected. A thorough analysis of all Grade 3 (or above) cases will be carried out by the sponsor's medical officer or designee, irrespective of whether the criteria for pausing the study are met. Based on the pausing criteria, the sponsor's medical officer or designee then decides whether a study pause is warranted. All sites will be notified immediately in case of a study pause. The sponsor's medical officer or designee is responsible for the immediate notification of DRC members and coordination of a DRC meeting in case of a study pause.

Vaccinations for an individual participant may be suspended for safety concerns other than those described in the pausing criteria, at the discretion of the investigator if he/she feels the participant's safety may be threatened. The sponsor's medical officer or designee or the investigator(s) (upon consultation with the sponsor's medical officer or designee) may initiate DRC review for any single event or combination of multiple events which, in their professional opinion, could jeopardize the safety of the participants or the reliability of the data.

Vaccinations for the study may be suspended for safety concerns other than those described above, or before pausing rules are met, if, in the judgment of the DRC, participant safety may be threatened.

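### The solicited-AE pausing trigger can be met from post-dose Day 4, but diaries are first scheduled for review on Day 8 to 10, and the contact on Days 4 to 6 is only for diary completion

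*Protocol*

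**What the plan says.** Criterion 6 of Protocol Section 6.8 has two limbs. The general limb is "Three or more participants experience a Grade 3 solicited AE of the same type, determined to be related to study vaccine". This limb also carries a duration condition, so that an event counts only when it is "persisting as Grade 3 for longer than 3 consecutive days", with the day of onset counted as Day 1. The sentinel limb is "one participant from sentinel cohort experiences a Grade 3 solicited systemic AE that is determined to be related to study vaccine", with no persistence condition.

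Solicited events are recorded by the participant in a diary. Section 4.1 says: "Study-site personnel will collect and review participant diary information and confirm the entries at subsequent site visits". The Schedule of Activities (Section 1.3.1) places diary review at Visit 3 (Day 8, +2 days) and Visit 6: "Day 64 should be calculated with respect to vaccination 2 = VAC 2 + 7 days (+ 2 days window". Section 8 adds that a missed review moves to the following visit, which would be Day 29 or Day 85.

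Section 6.8 requires the investigator to notify the sponsor "immediately and no later than 24 hours after becoming aware of any related AE of Grade 3 or above". The clock therefore runs from site awareness.

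Footnote b of the Schedule of Activities describes two kinds of contact before Day 8. For sentinels: "An additional telephone call will be made to sentinel participants 48 hours post-vaccination to collect safety information". For all participants, a call or other communication is made "3 to 5 days after Day 1 and Day 57 visits to ensure that participants are completing the diary without issues". The influenza-season calls (footnote m and Section 8.1.1) do have a safety purpose, since they check for SAEs.

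Under Section 4.1, the DRC reviews 7-day data on 17 participants in Cohort 1 and 15 in Cohort 2. After that, the remaining 43 and 95 are enrolled. The current text gives no further first-dose hold within a cohort, no daily cap and no accrual rate.

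**The concern.** Section 6.8 gives prompt response as the reason for its 24-hour rule, and Section 2.3.3 presents the pausing rules as protection for participants not yet exposed. A trigger that can be met on Day 4 serves those aims only as well as the site's route to learning of it. The scheduled route is a diary review on Day 8 to 10. The protocol already contacts every participant in between, at about the time a persisting Grade 3 reaction could first be known, but the stated purpose of that contact does not include asking about one. In a first-in-human study, dosing of the main subset could then continue for some days after the criterion had in fact been met.

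**Working it through.** **Subset sizes (Section 4.1).** Cohort 1: 5 + 12 + 43 = 60. Cohort 2: 5 + 10 + 95 = 110. Both agree with the planned totals. The main subsets hold 43 + 95 = 138 of 170 (81%). Active recipients in them number 18 + 18 = 36 and 4 × 22 = 88. Active recipients in the DRC-reviewed groups number 4 + 10 = 14 of 17 and 4 + 8 = 12 of 15.

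**Timing, with dosing on Day 1.**

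| Event | Study day | Days after dose |
|---|---|---|
| Persistence first met, onset Day 1 | 4 | 3 |
| Contact with all participants | 4 to 6 | 3 to 5 |
| Scheduled diary review | 8 to 10 | 7 to 9 |

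For a Day 1 onset, the gap from Day 4 to the diary review is 4 to 6 days. Matching the ends of the two windows (7 − 3 and 9 − 5), an informative contact would come 4 days earlier. A contact on Days 4 to 6 can confirm persistence only for onsets on Days 1 to 3.

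**Accrual.** The documents give no figure for accrual, time to recognition or number dosed before a pause, so there is nothing of the plan's to reproduce here. Suppose, as an extreme, that the first three dosed are all cases. Then more than half of a main subset is dosed within the lag only if accrual reaches (number just over half) ÷ lag:

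- Cohort 1, diary visit: 22/9 to 22/7 = 2.4 to 3.1 per day. With the contact: 22/5 to 22/3 = 4.4 to 7.3.
- Cohort 2, diary visit: 48/9 to 48/7 = 5.3 to 6.9 per day. With the contact: 48/5 to 48/3 = 9.6 to 16.

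**Simulation to the third case.** There were 4,000 runs per setting. Assumptions: uniform accrual; each main subset counted alone; qualifying cases of one type only in active recipients; recognition uniformly 7 to 9 days (diary) or 3 to 5 days (contact) after dosing; immediate pause at the third recognised case; no spontaneous reports. Medians are over runs that reach three cases. Results at a 20% qualifying rate, as median share of the main subset dosed at recognition:

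| Main subset | Accrual per day | Diary visit | Contact |
|---|---|---|---|
| Cohort 1 (43) | 1 | 53% | 44% |
| | 2 | 72% | 56% |
| | 3 | 91% | 63% |
| | 5 | 100% | 81% |
| Cohort 2 (95) | 2 | 32% | 23% |
| | 3 | 40% | 27% |
| | 5 | 57% | 36% |
| | 10 | 99% | 57% |

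At a 10% rate the shares are 95% against 77% in Cohort 1 at 2 per day, and 72% against 52% in Cohort 2 at 5 per day. In Cohort 1 at 8 per day or more with a 20% rate, both medians are 100% and the gain disappears.

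**DRC review before the main subset.** The chance that three or more qualifying cases are already present is 1 − Σ C(n,k) pᵏ(1 − p)ⁿ⁻ᵏ over k = 0, 1, 2. For n = 14 / 12 it is 0.16 / 0.11 at p = 10%, 0.55 / 0.44 at 20%, and 0.84 / 0.75 at 30%.

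**The case against.** The strongest reply is that scheduled diary review is one safeguard among several. Each main subset opens only after the DRC has seen 7-day data. At a 20% rate, that review would itself hold three qualifying cases about half the time, and the DRC may act on fewer. Section 6.8 lets the DRC suspend vaccination before any rule is met, and lets the medical officer or investigator start a DRC review over a single event. Every participant is observed for 30 minutes and carries a wallet card with a 24-hour number. Any spontaneous report, including one made during the Day 4 to 6 contact, already starts the 24-hour clock. High-dose second doses wait for review of low-dose second-dose data. The diary's own instructions and the DRC charter are not in the documents, so participants may be told to call. All of this stands. It lowers the risk, but it does not make the one universal early contact informative, and at a 10% rate the DRC review holds three cases only 11% to 16% of the time.

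It is also fair that waiting for a third case causes much of the exposure (77% remains in Cohort 1 at 10% and 2 per day even with the contact), and that a Day 4 contact may precede that day's diary entry. The contact figures are therefore best cases. Early knowledge still has a use, because Section 6.8 requires the sponsor to analyse every Grade 3 case whether or not a pausing criterion is met.

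A reader might infer that most of the main subset will be dosed before the trigger can be recognised. The documents do not support that. In Cohort 2 at 2 per day, the simulated chance that more than half are dosed is 0.42, 0.05 and 0.00 at rates of 10%, 20% and 30%. A reader might also call the pausing rules the only brake, or the site blind until Day 8; the safeguards above contradict both.

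**Conclusion.** The point holds as a gap in scheduled recognition. No two passages contradict each other, and the pausing rule itself is not shown to be wrong. The general limb of criterion 6 can be met from Day 4, scheduled diary review starts on Day 8 to 10, and the contact in between is limited to diary completion. The lag is about 4 days compared with an informative contact, and it matters chiefly for the 138 participants (81%) in the main subsets.

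The number dosed in that time cannot be fixed from the documents. The simulated shares rest on assumed accrual, an assumed qualifying rate, no spontaneous reports and an immediate pause, whereas Section 6.8 places a medical review first. Pooling cases across cohorts or carrying forward those from the DRC-reviewed groups would bring recognition earlier. The sentinel limb is partly covered by the 48-hour safety call, and the conclusion does not rest on it. The change is worth making because it is specific and costs almost nothing.

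**What to change.** In footnote b of Section 1.3.1, add to the stated purpose of the existing contact a question on whether any diary symptom has been recorded at Grade 3 or above and, if so, its start date. A positive answer goes to qualified, delegated staff for grading and to the investigator for causality, under the procedures already in footnote o, Section 8.3.2 and Appendix 4. Leave the pausing criteria, the notification rule and dosing as they are. If the diary instructions already ask participants to phone about severe symptoms, say so in the protocol.

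The cost is one question in at most two contacts per participant (2 × 170 = 340), with no added visit. Contacts made by means other than telephone must carry the same question, and positive answers need some qualified staff time. Some self-graded reports will later be downgraded at diary review.
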